## 5.2.1.2.3 Dose Modification for Radiation

Reversible radiation mucositis is expected to develop in the majority of patients. This will commonly manifest as Grades I to III in severity. In those rare cases of Grade IV mucositis, radiation can be interrupted for up to5 consecutive radiation treatment days until the reaction subsides to Grade III. However, every effort should be made to keep this treatment break as short as possible. If Grade IV mucositis occurs, systemic chemotherapy should also be held until the reaction subsides to Grade III and then radiation and chemotherapy are resumed.

Toxicities: Common radiation toxicities include mucositis, fatigue, weight loss, regional alopecia, xerostomia, hoarseness, transient ear discomfort, hypogeusia, dysgeusia, dysphagia, and skin erythema and desquamation within the treatment fields. Less common long-term radiation toxicities include hypothyroidism, loss of hearing, chronic swallowing dysfunction requiring permanent feeding tube, and cervical fibrosis. Much less common radiation toxicities include mandibular osteoradionecrosis (<5% incidence with attention to a full dental evaluation as part of pre-treatment planning), and cervical myelopathy (<1% with restriction of spinal cord dose to < 45 Gy).

## 5.2.1.3 Timing of Dose Administration

Trial treatment should be administered after all procedures/assessments have been completed as detailed on the Trial Flow Chart (Section 6.0). Trial treatment may be administered up to 4 days after the scheduled Day -7 treatment start date due to administrative reasons. Additional treatments may be delayed as outlined in Section 6.0.

## 5.2.1.3.1 Pembrolizumab

Pembrolizumab 200 mg will be administered as a 30 minute IV infusion every 3 weeks. Sites should make every effort to target infusion timing to be as close to 30 minutes as possible. However, given the variability of infusion pumps from site to site, a window of -5 minutes and +10 minutes is permitted (i.e., infusion time is 30 minutes: -5 min/+10 min).

On days in which cisplatin is to be administered the same day as pembrolizumab, pembrolizumab should be administered prior to the cisplatin. On days when pembrolizumab is to coincide only with radiation, pembrolizumab can be given prior to or after radiation.

The Pharmacy Manual contains specific instructions for the preparation of the pembrolizumab infusion fluid and administration of infusion solution.

# 5.2.1.3.2 Cisplatin

Cisplatin will be administered weekly (every 7 days) starting on day 1 of CRT. Treatment cannot begin until all study procedures and assessments are completed as outlined in the Trial Flow Chart (Section 6.0).

Cisplatin is to be given as a dose of 40 mg/m2 using an infusion duration of 60 minutes (or infusion duration according to local practice).

# 5.2.2 Radiation

IMRT planning will be used for this study.

# 5.2.2.1 **IMRT**

IMRT will be given as 70 Gy in 35 fractions over approximately 7 weeks. The primary tumor and involved nodes ( $PTV_{HD}$ ) will receive 2 Gy per fractions and subclinical disease sites ( $PTV_{ID}$ ) will receive 1.8 Gy per fraction. The total doses will thus be 70 Gy and 63 Gy, respectively. When desired,  $PTV_{ID}$  can receive 1.6 Gy per fractions to a total dose of 56 Gy ( $PTV_{LD}$ ).

All plans must be normalized such that 95% of the volume of the  $PTV_{HD}$  is covered with the prescription dose of 70Gy. Additionally:

- No more than 20% of the  $PTV_{HD}$  should receive  $\geq 110\%$  of the prescribed dose;
- No more than 1% of any PTVHD or PTVID should receive  $\leq$  93% of the prescribed dose;
- No more than 1% or 1 cc of the tissue outside the PTVs should receive  $\geq 110\%$  of the prescribed dose to the PTVHD.

## 5.2.2.2 Technical Factors

Photon beams of  $\geq$  4 MV and/or electron beams from 6-25 MeV are required. Treatment distance must be  $\geq$  80 cm SAD for isocentric techniques.

IMRT: Megavoltage equipment capable of delivering intensity modulated beams using a stepand-shoot technique with a multileaf collimator or using dynamically moving leaves. Additionally, a binary multileaf collimator or tomotherapy can be used to modulate the beam. Other techniques, e.g. physical compensators, are acceptable as long as dose specifications and constraints are satisfied.

# 5.2.2.3 Immobilization, Simulation, and Localization

#### 5.2.2.4 Immobilization

The use of a thermoplastic head and shoulder mask is mandatory for IMRT. The margins used for expansion of the CTVs to PTVs are discussed in Section 5.2.2.3.3.

## 5.2.2.5 Planning CT scan

A treatment planning CT scan is mandatory for defining target volumes (see Section 5.2.2.6). CT scan thickness should be at most 0.3 cm for IMRT. The treatment planning CT scan should be acquired with the patient in the same position and using the same immobilization device as for treatment. All tissues receiving irradiation should be included in the CT scan.

# 5.2.2.6 Treatment Planning/Target Volumes

CT based treatment planning is mandatory for every patient. For IMRT, the treatment plan used for each patient will be based on an analysis of the volumetric dose, including dose-volume histogram (DVH) analyses of the PTV (CTV with a 5 mm margin) and critical normal structures. An "inverse" planning with computerized optimization should be used.

Gross Tumor Volume (GTV) represents the region judged to contain gross primary tumor or involved node(s) based on clinical and endoscopic examinations, CT scan, and, when applicable, other imaging techniques. Grossly positive lymph nodes are defined as any lymph nodes > 1 cm or nodes with a necrotic center.

Clinical Target Volume (CTV) is defined as the GTV plus areas considered at risk for containing microscopic disease delineated by the treating physician.  $CTV_1$  represents GTV plus a margin of generally 1 cm and  $CTV_2$  represents GTV with a margin of about 2 cm and nodal regions to receive elective irradiation. When the tumor is infiltrative (endophytic) or when the border is ill defined, it might be desirable to deliver an intermediate dose (e.g., 59-63 Gy) to a volume ( $CTV_{INT}$ ) that is slightly larger than  $CTV_1$ . The CTV margins can be narrower when GTV is in the proximity of the spinal cord or critical normal tissues.

Planning Target Volume ( $PTV_{HD}$ ,  $PTV_{ID}$ ,  $PTV_{LD}$ ) represents an additional margin around  $CTV_1$  and  $CTV_2$  to compensate for the variability of treatment set up and internal organ motion. A minimum margin of 0.5 cm around the CTV is required in all directions to define each respective PTV, except for situations in which the CTV is adjacent to spinal cord or other critical normal tissues. In such situations, the margin can be reduced judiciously. A minimum margin of 3 mm can be used in all directions as long as an institution implements a study to define the appropriate magnitude of the uncertain components of the PTV.

## 5.2.2.7 Critical Structures

Spinal cord: A margin of 0.5-1cm around the spinal cord may be added to create a Planning Organ at Risk Volume (PRV). The dose to any point within the spinal cord should not exceed 48 Gy to any volume larger than 0.03 cc (approximately equivalent to a 3x3x3 mm cube).

Parotid glands: When using IMRT, the objective is to limit the mean dose to at least one gland to  $\leq 26$  Gy; alternatively at least 20 cc of the combined volume of both parotid glands to < 20 Gy or at least 50% of one gland to <30 Gy.

Glottic larynx: In patients with oropharyngeal carcinoma without extension to the larynx, placing the isocenter just above the arytenoids and irradiating the lower neck with an anterior matching field with larynx block can minimize the dose to the glottic larynx. Alternatively, the dose to the larynx should be kept <45 Gy whenever feasible.

Brachial plexus: The dose to the brachial plexus must be limited to  $\leq 60$  Gy in patients with level IV node(s).based on a dose distribution corrected for heterogeneities.

Unspecified tissue outside the target volumes:  $\leq 100\%$  of the dose prescribed to CTV1. No more than 5% of the non-target tissue can receive greater than the dose to CTV1.

#### 5.2.2.8 **Documentation Requirements**

Portal image of each field of 3-D radiotherapy or orthogonal images that localize the isocenter placement of IMRT must be obtained on the first day of therapy.

Weekly verification or orthogonal images are required.

Isodose plans for IMRT and DVHs of GTV, CTVs, and critical normal structures for IMRT.

## 5.2.2.9 Compliance Criteria

Treatment breaks must be clearly indicated in the treatment record along with the reason(s) for the treatment break(s). Missed treatments due to holidays or logistic reasons can be compensated for by delivering additional BID treatments with a minimum interfraction interval of 6 hours or by treating on a Saturday or Sunday.

Treatment breaks should be allowed only for resolution of severe acute toxicity and/or for intercurrent illness and ideally, should not exceed 5 treatment days at a time and 10 treatment days in total. Any treatment break(s) exceeding two treatment days for reasons other than toxicity/illness will be considered a protocol deviation.

Plan normalization should provide coverage of 95% of the volume of the PTV of the GTV (PTVHD) with the prescribed dose of 70 Gy. No more than 1% of the volume of the PTVHD should receive less than 64 Gy. Additionally, no more than 10% of the PTV of the GTV should receive more than 76 Gy, and no more than 5% of this volume should receive more than 79 Gy. These numbers describe the DVH shown in the figure below with the diamond shaped symbols. Obviously, better DVHs (i.e., with smaller amounts of either underdose or overdose) are preferable.

A region of "minor deviation" is also defined in the figure as the DVH represented by the square symbols. Deviations of this magnitude are not desirable, but will be deemed acceptable.

That is, a DVH with at least 97% of the volume receiving 64 Gy is acceptable as a minor deviation.

[figure not shown]
Additionally, as a minor deviation for the overdose region, as much as 40% of the PTVHD volume can receive 76 Gy and up to 10% of this volume can receive 79 Gy. DVHs for the PTVHD falling outside the limits for a minor deviation (i.e., increased under or overdose) will be scored as unacceptable "major deviations."

The DVHs for the other target regions should deliver the prescribed dose, as much as possible, to at least 95% of the volume of that PTV.

Overall Evaluation	Radiotherapy Prolongation	Total Dose Variation IMRT**
Per Protocol	≤5 days	See parameters in the figure below
Minor Variation (Acceptable)	6-10 days	See parameters in the figure and table below
Major Deviation (Unacceptable)	>10 days	Deviations greater than presented in the table and figure below

\*\*Note: For IMRT, prescription dose is the isodose surface that encompasses at least 95% of the planning target volume (PTV) with no more than 10% of any  $PTV_{HD}$  receiving  $\geq 110\%$  of the prescribed dose and no more than 1% of any  $PTV_{HD}$  and  $PTV_{ID}$  receiving  $\leq 93\%$  of the prescribed dose.

Dose (Gy)	Per Prescription	Minor variation
65	99%	97%
70	95%	95%
77	20%	40%
80	5%	20%

#### 5.3 Trial Blinding/Masking

This is an open-label trial; therefore, Sanford Research, investigator and subject will know the treatment administered.

#### 5.4 **Randomization or Treatment Allocation**

The study is non-randomized. There is only one treatment arm. All subjects will receive the study treatment.

#### 5.5 Stratification

•

There are two separate cohorts of subjects in this clinical trial. Thirty-four of the 57 subjects will be HPV+ while the remaining 23 subjects will be HPV-.

#### 5.6 **Concomitant Medications/Vaccinations (allowed & prohibited)**

Medications or vaccinations specifically prohibited in the exclusion criteria are not allowed during the ongoing trial. If there is a clinical indication for one of these or other medications or vaccinations specifically prohibited during the trial, discontinuation from trial therapy or vaccination may be required. The investigator should discuss any questions regarding this with the Principal Investigator. The final decision on any supportive therapy or vaccination rests with the investigator and/or the subject's primary physician.

#### 5.6.1 Acceptable Concomitant Medications

All treatments that the investigator considers necessary for a subject's welfare may be administered at the discretion of the investigator in keeping with the community standards of medical care. All concomitant medication will be recorded on the case report form (CRF) including all prescription, over-the-counter (OTC), herbal supplements, and IV medications and fluids. If changes occur during the trial period, documentation of drug dosage, frequency, route, and date may also be included on the CRF.

All concomitant medications received within 28 days before the first dose of trial treatment and 30 days after the last dose of trial treatment should be recorded. Concomitant medications administered after 30 days after the last dose of trial treatment should be recorded for SAEs and ECIs as defined in Section 7.2.

#### 5.6.2 **Prohibited Concomitant Medications**

Subjects are prohibited from receiving the following therapies during the Screening and Treatment Phase of this trial:

- Antineoplastic systemic chemotherapy or biological therapy
- Immunotherapy not specified in this protocol
- Chemotherapy not specified in this protocol
- Investigational agents other than pembrolizumab
- Radiation therapy not specified in this protocol
- Live vaccines within 30 days prior to the first dose of trial treatment and while participating in the trial. Examples of live vaccines include, but are not limited to, the following: measles, mumps, rubella, varicella/zoster, yellow fever, rabies, BCG, and typhoid vaccine.
- Systemic glucocorticoids for any purpose other than to modulate symptoms from an event of clinical interest of suspected immunologic etiology. The use of physiologic doses of corticosteroids may be approved after consultation with the study Principal Investigator or designee.

Subjects who, in the assessment by the investigator, require the use of any of the aforementioned treatments for clinical management should be removed from the trial. Subjects may receive other medications that the investigator deems to be medically necessary.

The Exclusion Criteria describes other medications which are prohibited in this trial.

#### 5.7 **Rescue Medications & Supportive Care**

#### 5.7.1 Supportive Care Guidelines for Pembrolizumab

Subjects should receive appropriate supportive care measures as deemed necessary by the treating investigator. Suggested supportive care measures for the management of adverse events with potential immunologic etiology are outlined below and in greater detail in the ECI guidance document. Where appropriate, these guidelines include the use of oral or intravenous treatment with corticosteroids as well as additional anti-inflammatory agents if symptoms do not improve with administration of corticosteroids. Note that several courses of steroid tapering may be necessary as symptoms may worsen when the steroid dose is decreased. For each disorder, attempts should be made to rule out other causes such as metastatic disease or bacterial or viral infection, which might require additional supportive care. The treatment guidelines are intended to be applied when the investigator determines the events to be related to pembrolizumab.

Note: if after the evaluation the event is determined not to be related, the investigator is instructed to follow the ECI reporting guidance but does not need to follow the treatment guidance (as outlined in the ECI guidance document). Refer to Section 5.2.1 for dose modification.

- It may be necessary to perform conditional procedures such as bronchoscopy, endoscopy, or skin photography as part of evaluation of the event. Suggested conditional procedures, as appropriate, can be found in the ECI guidance document.
- Pneumonitis:
  - For **Grade 2 events**, treat with systemic corticosteroids. When symptoms improve to Grade 1 or less, steroid taper should be started and continued over no less than 4 weeks.
  - For **Grade 3-4 events**, immediately treat with intravenous steroids. Administer additional anti-inflammatory measures, as needed.
  - Add prophylactic antibiotics for opportunistic infections in the case of prolonged steroid administration.

#### • Diarrhea/Colitis:

Subjects should be carefully monitored for signs and symptoms of enterocolitis (such as diarrhea, abdominal pain, blood or mucus in stool, with or without fever) and of bowel perforation (such as peritoneal signs and ileus).

• All subjects who experience diarrhea/colitis should be advised to drink liberal quantities of clear fluids. If sufficient oral fluid intake is not feasible, fluid and

electrolytes should be substituted via IV infusion. For Grade 2 or higher diarrhea, consider GI consultation and endoscopy to confirm or rule out colitis.

- For **Grade 2 diarrhea/colitis** that persists greater than 3 days, administer oral corticosteroids.
- For **Grade 3 or 4 diarrhea/colitis** that persists > 1 week, treat with intravenous steroids followed by high dose oral steroids.
- When symptoms improve to Grade 1 or less, steroid taper should be started and continued over no less than 4 weeks.
- Type 1 diabetes mellitus (if new onset, including diabetic ketoacidosis [DKA]) or ≥ Grade 3 Hyperglycemia, if associated with ketosis (ketonuria) or metabolic acidosis (DKA)
  - For **T1DM** or **Grade 3-4** Hyperglycemia
    - Insulin replacement therapy is recommended for Type I diabetes mellitus and for Grade 3-4 hyperglycemia associated with metabolic acidosis or ketonuria.
    - Evaluate patients with serum glucose and a metabolic panel, urine ketones, glycosylated hemoglobin, and C-peptide.
- Hypophysitis:
  - For Grade 2 events, treat with corticosteroids. When symptoms improve to Grade 1 or less, steroid taper should be started and continued over no less than 4 weeks. Replacement of appropriate hormones may be required as the steroid dose is tapered.
  - For **Grade 3-4** events, treat with an initial dose of IV corticosteroids followed by oral corticosteroids. When symptoms improve to Grade 1 or less, steroid taper should be started and continued over no less than 4 weeks. Replacement of appropriate hormones may be required as the steroid dose is tapered.

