#### • Hyperthyroidism or Hypothyroidism:

Thyroid disorders can occur at any time during treatment. Monitor patients for changes in thyroid function (at the start of treatment, periodically during treatment, and as indicated based on clinical evaluation) and for clinical signs and symptoms of thyroid disorders.

- Grade 2 hyperthyroidism events (and Grade 3-4 hypothyroidism):
  - In hyperthyroidism, non-selective beta-blockers (e.g. propranolol) are suggested as initial therapy.
  - In hypothyroidism, thyroid hormone replacement therapy, with levothyroxine or liothyroinine, is indicated per standard of care.
- Grade 3-4 hyperthyroidism
  - Treat with an initial dose of IV corticosteroid followed by oral corticosteroids. When symptoms improve to Grade 1 or less, steroid

taper should be started and continued over no less than 4 weeks. Replacement of appropriate hormones may be required as the steroid dose is tapered.

- Hepatic:
  - For **Grade 2** events, monitor liver function tests more frequently until returned to baseline values (consider weekly).
    - Treat with IV or oral corticosteroids
  - For Grade 3-4 events, treat with intravenous corticosteroids for 24 to 48 hours.
  - When symptoms improve to Grade 1 or less, a steroid taper should be started and continued over no less than 4 weeks.

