#### • Renal Failure or Nephritis:

- For Grade 2 events, treat with corticosteroids.
- For Grade 3-4 events, treat with systemic corticosteroids.
- When symptoms improve to Grade 1 or less, steroid taper should be started and continued over no less than 4 weeks.

**Management of Infusion Reactions**: Signs and symptoms usually develop during or shortly after drug infusion and generally resolve completely within 24 hours of completion of infusion.

Table 4 below shows treatment guidelines for subjects who experience an infusion reaction associated with administration of pembrolizumab (MK-3475).

	ease monitoring of vital signs as medically cated until the subject is deemed medically le in the opinion of the investigator.	None
not indicated; intervention not stabl indicated		
Requires infusion interruption but responds promptly to symptomatic treatment (e.g., antihistamines, NSAIDS, narcotics, IV fluids); prophylactic medications indicated for <=24 hrs	D Infusion and monitor symptoms. litional appropriate medical therapy may ude but is not limited to: IV fluids Antihistamines NSAIDS Acetaminophen Narcotics ease monitoring of vital signs as medically cated until the subject is deemed medically le in the opinion of the investigator. rmptoms resolve within one hour of stopping g infusion, the infusion may be restarted at to of the original infusion rate (e.g., from 100 hr to 50 mL/hr). Otherwise dosing will be until symptoms resolve and the subject ild be premedicated for the next scheduled c. jects who develop Grade 2 toxicity despite quate premedication should be manently discontinued from further trial tment administration.	Subject may be premedicated 1.5h (± 30 minutes) prior to infusion of pembrolizumab (MK-3475) with: Diphenhydramine 50 mg po (or equivalent dose of antihistamine). Acetaminophen 500-1000 mg po (or equivalent dose of antipyretic).

 Table 4 Infusion Reaction Treatment Guidelines

NCI CTCAE Grade	Treatment	Premedication at subsequent dosing
Grades 3 or 4	Stop Infusion.	No subsequent dosing
Grade 3: Prolonged (i.e., not rapidly responsive to symptomatic medication and/or brief interruption of infusion); recurrence of symptoms following initial improvement; hospitalization indicated for other clinical sequelae (e.g., renal impairment, pulmonary infiltrates)	Additional appropriate medical therapy may include but is not limited to: IV fluids Antihistamines NSAIDS Acetaminophen Narcotics Oxygen Pressors Corticosteroids Epinephrine	

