## 7.2.4.1 Table 6 Evaluating Adverse Events

An investigator, who is a qualified physician, will evaluate all adverse events as to:

V4.0 CTCAE Grading	Grade 1	Mild; asymptomatic or mid symptoms; clinical or diagnostic observations only; intervention not indicated.							
Grading	Grade 2	Moderate; minimal, local or noninvasive intervention indicated; limiting age-appropriate instrumental ADL.							
	Grade 3	Severe or medically significant but not immediately life-threatening; hospitalization or prolongation or hospitalization indicated;							
		disabling; limiting self-care ADL.							
	Grade 4	Life threatening consequences; urgent intervention indicated.							
	Grade 5	Death related to AE							
Seriousness	A serious adverse event is any adverse event occurring at any dose or during any use of Merck product that:								
	†Results in death ;	or							
	†Is life threatenin	g; or places the subject, in the view of the investigator, at immediate risk of death from the event as it occurred (Note: This does not include an							
		had it occurred in a more severe form, might have caused death.); or							
		istent or significant disability/incapacity (substantial disruption of one's ability to conduct normal life functions); or							
	†Results in or prolongs an existing inpatient hospitalization (hospitalization is defined as an inpatient admission, regardless of length of stay, even if the								
	hospitalization is a precautionary measure for continued observation. (Note: Hospitalization [including hospitalization for an elective procedure] for a preexisting								
	condition which has not worsened does not constitute a serious adverse event.); or								
	†Is a congenital anomaly/birth defect (in offspring of subject taking the product regardless of time to diagnosis);or								
	Is a new cancer; (that is not a condition of the study) or								
	Is an overdose (whether accidental or intentional). Any adverse event associated with an overdose is considered a serious adverse event. An overdose that is not								
	associated with an adverse event is considered a non-serious event of clinical interest and must be reported within 24 hours.								
	Other important medical events that may not result in death, not be life threatening, or not require hospitalization may be considered a serious adverse event when,								

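### Section 5.7.1 suggests starting steroids 4 days later for Grade 3-4 diarrhea/colitis (over 1 week) than for Grade 2 (over 3 days), and no other Grade 3-4 steroid instruction for an organ toxicity there has a wait

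*Combined protocol and SAP*

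**What the plan says.** Under Diarrhea/Colitis, section 5.7.1 gives two adjacent steroid bullets. For Grade 2 the text is "that persists greater than 3 days, administer oral corticosteroids". For Grade 3 or 4 it is "that persists > 1 week, treat with intravenous steroids followed by high dose oral steroids". Neither bullet says what to do when an episode changes grade, or whether the week runs from the start of the episode or from the start of Grade 3.

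The other Grade 3-4 steroid instructions for organ toxicities in the same section state no waiting period. Pneumonitis reads "immediately treat with intravenous steroids", the hepatic bullet reads "treat with intravenous corticosteroids for 24 to 48 hours", and the renal bullet reads "For Grade 3-4 events, treat with systemic corticosteroids". Hypophysitis and hyperthyroidism call for an initial IV dose followed by oral treatment, again with no wait.

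Table 6 (7.2.4.1) defines Grade 4 as "Life threatening consequences; urgent intervention indicated".

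Two passages set the status of this guidance. Section 5.7.1 opens with "Suggested supportive care measures for the management of adverse events with potential immunologic etiology are outlined below" and refers to the ECI guidance document for more detail. The list of prohibited medications in 5.6.2 includes "Systemic glucocorticoids for any purpose other than to modulate symptoms from an event of clinical interest of suspected immunologic etiology", so steroids for a suspected immune event remain permitted at any time.

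**The concern.** The two colitis bullets run against the order of severity: the milder event reaches its steroid trigger first. A site that follows them literally would start treatment later in the patient at greater risk. The same part of 5.7.1 tells sites to watch for bowel perforation.

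A worsening episode is the awkward case. A patient who moves from Grade 2 to Grade 3 on or before day 3 has not yet met the Grade 2 trigger and passes to the later one. Section 7.2.4 expects grade changes within an episode and requires each to be recorded, so this is foreseeable.

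Safety and tolerability is the first primary objective (3.1), and 4.2.3.1 singles out immune-related toxicity for particular attention. The trial is multi-site, so the in-protocol text should give sites a consistent and correctly ordered instruction. The stake is patient safety; no endpoint definition, power figure or error rate depends on it.

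**Working it through.** The protocol gives no summary figure to reproduce. The check is a reading of every Grade 3-4 instruction in 5.7.1, plus simple day counts.

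**Step 1: the gap at constant grade.**
- Grade 2 trigger: more than 3 days (5.7.1, Diarrhea/Colitis).
- Grade 3 or 4 trigger: more than 1 week, that is 7 days (same place).
- Gap = 7 - 3 = **4 days later** for the more severe grade.

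**Step 2: an episode that worsens to Grade 3 on day d, with d = 1, 2 or 3.** Had the patient stayed at Grade 2, steroids would start after day 3.
- If the week counts from episode onset: start after day 7; delay = 7 - 3 = 4 days for any d.
- If the week counts from Grade 3 onset: start after day d + 7; delay = (d + 7) - 3 = d + 4.

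| Day of worsening (d) | Start, week from episode onset | Delay | Start, week from Grade 3 onset | Delay |
|---|---|---|---|---|
| 1 | after day 7 | 4 days | after day 8 | 5 days |
| 2 | after day 7 | 4 days | after day 9 | 6 days |
| 3 | after day 7 | 4 days | after day 10 | 7 days |

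The text does not choose between the two clocks. The 5 to 7 day figures are therefore conditional on one reading and on the assumed day of worsening.

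**Step 3: comparison with the other Grade 3-4 steroid instructions in 5.7.1.**

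| Event | Grade 3-4 steroid instruction | Waiting period |
|---|---|---|
| Pneumonitis | IV, at once | None |
| Diarrhea/colitis | IV, then high-dose oral | More than 1 week |
| Hypophysitis | Initial IV dose, then oral | None |
| Hyperthyroidism | Initial IV dose, then oral | None |
| Hepatic | IV for 24 to 48 hours | None (the hours are a treatment duration) |
| Renal failure/nephritis | Systemic | None |

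One of 6 has a wait. Adding the infusion reaction table (Table 4), where corticosteroids are a listed option for Grade 3-4 with no wait, makes it 1 of 7. Type 1 diabetes/hyperglycemia and hypothyroidism have no steroid instruction and are not counted.

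**Step 4: could the wait be a diagnostic pause?** Section 5.7.1 applies its treatment guidance once the investigator has judged the event related to pembrolizumab, so attribution comes before the bullets. Its advice to exclude other causes covers every disorder listed, yet only colitis has a Grade 3-4 wait. A diagnostic rationale would also not explain a shorter wait at Grade 2.

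**The case against.** The case on the other side concerns weight, not wording.

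- **The fuller guidance is elsewhere.** Sections 5.2.1.2.1, 5.7.1, 7.1.2.1 and 7.2.3.2 all send sites to the ECI guidance document, which was not supplied. It may already give an earlier trigger. This stands as a limit: one cannot say that sites lack an earlier trigger. But if that document does give one, the protocol contradicts it and still needs correcting.
- **The measures are suggestions.** Care is left to the treating investigator, and 5.6.2 does not bar earlier steroids. This stands, and it lowers the likely harm. It does not justify guidance in the wrong order.
- **An escalation reading.** The bullets could mean oral steroids after 3 days at Grade 2 or above, then IV and high-dose oral treatment if Grade 3-4 persists beyond a week. This does not fit the text, because the first bullet is limited to Grade 2. It does remain true that a patient already on oral steroids who worsens is not told to stop them.
- **The comparison with other events is imperfect.** Colitis is the only event in 5.7.1 with a persistence condition at any grade, so part of the contrast is that colitis is handled differently throughout. That is fair. The reversal within colitis carries the point, and the comparison supports it.
- **Other safeguards act without a wait.** Table 3 holds pembrolizumab at Grade 2-3 and stops it permanently at Grade 4; GI consultation and endoscopy are to be considered from Grade 2; serious events go to the DSMB as soon as possible (7.3.2). These reduce the risk, but holding the drug is not treatment of established colitis.

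**Conclusion.** The concern holds and should be fixed. Section 5.7.1 places the suggested steroid start for Grade 3-4 diarrhea/colitis 4 days after that for Grade 2, and this is the only one of its six organ-specific Grade 3-4 steroid instructions with a waiting period. For an episode that worsens by day 3, the literal delay is 4 days on one clock and 5 to 7 on the other.

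The conclusion rests on reading the two bullets as written and on the supplied text alone. Confidence in the wording and the gap is high. The effect on patients is unknown: the documents give no number of Grade 3-4 colitis events, and investigators are free to treat earlier. This is a correction to safety text, with no consequence for sample size, power or type I error.

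**What to change.** Amend the Grade 3 or 4 diarrhea/colitis bullet in 5.7.1 so that its trigger can never fall later than the Grade 2 trigger. The simplest change is to delete the one-week persistence condition, which brings it into line with the other five organ-specific Grade 3-4 steroid instructions. Add a sentence that the highest current grade governs when an episode changes grade; this also removes the question of which day the clock starts. Check the new wording against the ECI guidance document before release, so that the two agree, and notify sites.

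The cost is one line in a protocol amendment and a site memo, with no extra data or patients. The downside is slightly more early steroid use in Grade 3-4 events, in a trial that otherwise limits steroids, but only in events for which 5.7.1 already suggests them.
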